A study comparing continuous restriction and 5-2 CR in overweight women, defined as 2 consecutive days of consuming 500-600 kilocalories followed by non-restricted eating for 5 days, indicated that both regimens produced comparable effects to alternate day restriction.⁴⁰ Both continuous CR and 5-2 CR were tailored to result in a net 20% energy restriction. Critically, 5-2 CR led to significantly higher insulin sensitivity relative to continuous restriction and was easier for participants to maintain. We previously showed that 8 weeks of alternate day CR induces multiple effects of interest,³⁹ such as decreased weight (~8% of baseline body weight), decreased TNF- α (Figure 1), and decreased levels of ROS-induced 8-isoprostanate, protein carbonyl, and nitrotyrosine (Figure 2).

[figure not shown]

Figure 1. The effect of alternate day calorie restriction on serum TNF- α . By the 8-week time point, concentrations were greatly reduced regardless of assessment on ad libitum (AL) or restricted (CR) days.

[figure not shown]

Figure 2. The effect of alternate day calorie restriction on serum levels of nitrotyrosine. By the 8-week time point levels decreased regardless of assessment on ad libitum (AL) or restricted (CR) days.

Study aims and overview

This study is a proof-of-concept exploratory pilot study, which will generate several kinds of preliminary data to guide further studies in the field. Using a randomized clinical trial design, we will compare the effects of 5-2 CR and a control diet. We will compare various outcome measures between groups, but also to baseline on a within-groups basis.

The following main outcomes will be assessed: 1) The ratio of Tyr and Ser phosphorylated forms (p-panY and pSer312) of insulin receptor substrate 1 (IRS-1) in plasma exosomes enriched for neuronal origin, which is a novel biomarker of brain IR (primary) (44); 2) peripheral insulin sensitivity derived from a mixed meal tolerance test;

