4.a.2. Compliance: We will assess and reinforce diet compliance with correspondence by telephone or electronic mail on week 1, 3, 5 and 7, as well as with Compliance Visits on weeks 2, 4, and 6. To assess compliance during Compliance Visits, we will be measuring plasma β -hydroxybutyrate. Values around 2-2.5 μ M/mL during CR days suggests compliance during 5-2 CR. β -hydroxybutyrate values of 0.5-1.0 μ M/mL suggest non-compliance with 5-2 CR, but would be expected for non restricted days and for the

control group.³⁹ In addition, we will be measuring body weight. Weight loss for 5-2 CR is expected to be about 2% per week based on our previous work.³⁹ Therefore, a progressive decrease seen after 2 weeks of 5-2 CR and persisting in the 5-2 CR group over 8 weeks suggest compliance to 5-2 CR,³⁹ while a smaller decrease in body weight is expected for the control group.

In addition, we will contact participants by telephone or electronic mail (using the Secure Email & File Transfer Service: <https://secureemail.nih.gov/bds/Login.do>) weekly to assess not only compliance with the diets, but also mood, level of energy, difficulty concentrating, headaches, feeling cold, constipation, negative emotions (sadness/depression, anxiety, irritability), hunger and preoccupation with food.^{39,40,94} For e-mail communications, we will provide participants with the web-address of the Secure Email & File Transfer Service with instructions on how to acquire login credentials.

4.b. Recruitment

Participants may be recruited through direct advertisement. Brochures and flyers will be used. Recruitment letters may be mailed to health care providers and to those participants who have requested information. We may place ads and/or public service announcements (PSA) on websites, in radio broadcasts, television, as well as newspapers, newsletters, and magazines. Direct mailing through established marketing and advertising organizations might also be used. Pre-screening over the telephone will utilize the eligibility checklist. Participants that we believe are likely to be eligible will come to the NIA-Clinical Research Unit to undergo screening.

We anticipate an accrual rate of 2-6 participants per month.

4.c. Screening

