The study is comprised of: an initial telephone pre-screening to describe the study and inclusion/exclusion criteria to potential participants; a "Screening Visit"; randomization into one of two groups; a "Baseline Visit"; the "Outcome Visit" after 8 weeks. During the 8-week period for the 5-2 CR or control groups, participants will return every two weeks for "Compliance Visits", to assess and reinforce dietary compliance in keeping with previous protocols.^{39,40,94} The Outcome Visit will take place at the conclusion of the 8-week phase. Specifically for the 5-2 CR group, the Outcome Visit will be timed during the second of the two CR days. In total, there will be 6 outpatient visits to the NIA Clinical Unit: Screening Visit, Baseline Visit, Week 2 Compliance Visit, Week 4 Compliance Visit, Week 6 Compliance Visit, and the Week 8 Outcome Visit. There will be an additional follow-up phone call or electronic mail within 3 days of completing the Week 8 Visit to assess any problems related to their final visit. Accelerometry will be implemented on two occasions for 96 hours each time: once between the screening and baseline visits and again after the Week 8 Outcome Visit. Throughout the study, additional safety visits may take place for any clinically significant. Participants will be involved in the study for approximately 8 – 11 weeks (allowing for an up to 3 week gap between Screening and Baseline Visits). Study participation will end with completion of accelerometry after the Week 8 Outcome Visit.

It is anticipated that participants in this study will occasionally miss or fail to complete an assessment or procedure, such as a completion of a rating scale or a blood draw. Omissions such as these will be considered expected events and not protocol deviations provided they are infrequent and do not include data needed to assess safety or the primary study outcome. Cumulative proportions of these missed events in the study population will be presented to the IRB annually. In addition, the rate of omissions will be monitored by the Investigators. If an individual misses more than 15% of the required assessments/procedures or if more than 15% of the participants miss completion of the same assessment or procedure, it will be considered a deviation and a deviation report

will be sent to the IRB within two weeks.

Table 1: Procedures

Procedures	Visit 1	Visit 2		Visit 3, 4, 5	Visit 6	
		Week 0		Weeks 2, 4, 6	Week 8	

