No major adverse effects have been associated with mild to moderate intermittent calorie restriction.^{39,40,94} Two of our previous CR studies did not have a reported serious AE incident.^{39,40} More severe caloric restriction in humans relative to our studies also produced no serious AEs⁹⁴. We classify the 5-2 CR and control diet as minimal risk.

8. Subject safety monitoring

8.a. Monitoring of Subjects

The investigator or clinical staff performing a study procedure will monitor subject safety. This includes physicians, licensed practitioners (NPs) and RNs during LPs, blood draws, mixed meal testing, and History and Physical sessions; investigators administering questionnaires and cognitive testing, MRI techs and investigators during MRIs.

The PI will make determinations regarding the presence and grading of on adverse events (AEs) and unanticipated problems (UPs). Whenever study investigators contact subjects throughout the study, they will seek information on AEs and UPs. AE's and UPs will also be elicited during study visits, by subjects filling in the symptoms review questionnaire or during history and physical examination. Participants will be asked to use electronic mail (Secure Email & File Transfer Service: <https://secureemail.nih.gov/bds/Login.do>) or telephone to inform the investigators about any AE's or UPs experienced. AEs and UPs may be observed by the Investigator and/or study staff, elicited from the subject and/or family member, or volunteered by the study subject. AEs and UP's that had previously been reported by study subject will also be reassessed for duration, intensity and

possible reoccurrence. Assessment of safety will include vital signs, history and physical sessions, questionnaires on physical and psychological symptoms and clinical labs as indicated. Any AE or UP that occurs between the times a study participant signs the informed consent form and the end of participation will be assessed and recorded under NIH HRPP SOP # 16 and 16 A.

In particular, we will monitor the weight loss of the participant. If a participant on 5-2 CR loses 4-5% of their body weight within a 2-week period between visits, additional safety visits will be scheduled every week to monitor body weight more closely. If weight loss in that range or greater continues to occur, participants will be removed from the study.

A study participant will also be discontinued from the study if:

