Plasma ketones are strongly affected by alternate day CR acutely but not chronically;³⁹ our main objective for measuring them is to assess compliance with 5-2 CR.

We do not anticipate a change in physical activity in 5-2 CR versus “healthy living” control groups, because no change has been noted in our previous studies. Nonetheless, this is a common analysis requested by reviewers, to make sure that exercise effects did not contaminate diet effects.

The data from the gene array and DNA methylation array will be analyzed using residuals after adjustment for white blood cell differential count in linear regression models. We will take two approaches to analyze the data. First we will focus on candidate genes approach where we select specific expression probe or CpG sites; DNA for these studies will be collected during Baseline, Compliance and Outcome Visits. Second, we will run genome-wide association analysis for differences in cross sectional and longitudinal changes in gene expression or DNA methylation between the control and 5-2 CR group at each gene array probe or CpG site. DNA for genome-wide association analyses will only be collected during Baseline and Outcome Visits. For the cross sectional analyses, we will use a paired t-test at each visit, and mixed models for longitudinal analysis. In addition, we will look at overall patterns of gene expression and methylation using principle components, DIANE and hierarchical clustering tools to determine whether there are specific gene expression and methylation signature in association with 5-2 CR. As secondary analyses, we will also determine whether gene expression and DNA methylation patterns can predict the changes in metabolic, cognitive and neurochemical variables collected in this study. Within the 5-2 CR group, we will test the association between baseline levels of gene expression or DNA methylations at each probe/CpG site with longitudinal changes in the main outcome variables using mixed models.

10. b. Power analysis

The accrual number request is 100 participants. Our target sample size for completing the study is $N = 40$. There will be 20 participants in each group. We anticipate up to 60 participants will not meet inclusion criteria during the screening visit or may withdraw from the study. Enrollment will continue and withdrawals will be replaced until we have acquired complete data from 40 participants.

For power calculations, we used G*Power (<http://www.gpower.hhu.de/en.html>).

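### The weekly-visit trigger in section 8.a is worded as a closed 4-5% band, so read literally a first 2-week loss above 5% requires no interim weighing (minor wording error in a safety threshold)

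*Combined protocol and SAP*

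**What the plan says.** Section 8.a (Monitoring of Subjects) has two consecutive rules on weight in the 5-2 CR arm.

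- Trigger: if a participant "loses 4-5% of their body weight within a 2-week period between visits, additional safety visits will be scheduled every week".
- Removal: "If weight loss in that range or greater continues to occur, participants will be removed from the study".

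The routine schedule is in section 4.a.2 (Compliance). Remote contact is set out as "We will assess and reinforce diet compliance with correspondence by telephone or electronic mail on week 1, 3, 5 and 7", and clinic attendance follows "as well as with Compliance Visits on weeks 2, 4, and 6". Weight is measured at the clinic visits (sections 4.a.2 and 4.d.4). The remote contacts cover adherence, mood and symptoms, with no weighing.

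Section 4.d.1 has a general provision: "Throughout the study, additional safety visits may take place for any clinically significant". The sentence is incomplete in the text available, so its scope cannot be judged. What can be read is permissive and sets no weight limit or weekly schedule.

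**The concern.** The two rules differ in one respect that matters. The removal rule covers the 4-5% range and anything larger. The trigger covers the range only. Because removal depends on the loss continuing, a first 2-week loss above 5% meets neither rule as written.

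Taken literally, the plan requires less weighing of the faster loser than of the slower one, which is the reverse of the purpose of a weight-safety rule. Section 15.a makes the principal investigator the data and safety monitor, and section 16.b has a delegate audit a sample of charts for adherence to procedures. Both tasks are easier if the threshold has one reading. Nothing in the randomisation, primary outcome, analysis or power is involved.

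**Working it through.** The plan gives no calculation for this threshold, so there is no figure to reproduce. The check has three parts.

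**1. Apply the rule as written and as it would read with a floor.**

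| First 2-week loss | Literal rule (4% ≤ loss ≤ 5%) | Floor rule (loss ≥ 4%) |
|---|---|---|
| 3.9% | no weekly visits | no weekly visits |
| 4.0% | weekly visits | weekly visits |
| 4.5% | weekly visits | weekly visits |
| 5.0% | weekly visits | weekly visits |
| 5.1% | no weekly visits | weekly visits |
| 6.0% | no weekly visits | weekly visits |
| 8.0% | no weekly visits | weekly visits |

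The readings differ only above 5%.

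**2. Look for other text that requires an interim weighing.** The contacts at weeks 1, 3, 5 and 7 are remote. The extra safety visits in 4.d.1 are discretionary. The other discontinuation criteria in 8.a (a possibly related adverse event of Grade 2 or above, a newly met exclusion criterion, persistent non-compliance) set no weight threshold. None of them requires a weighing between 2-weekly visits.

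The size of the gap depends on when the loss is first seen. Section 8.a does not say when weekly visits stop, so the count runs from one weighing, if they end at the next 2-weekly visit, to all remaining odd weeks:

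- first seen at week 2: week 3, or weeks 3, 5 and 7 (one to three weighings);
- first seen at week 4: week 5, or weeks 5 and 7 (one to two);
- first seen at week 6: week 7 (one).

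**3. Ask how often a loss above 5% might occur.** The documents contain three figures on pace.

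- Introduction, earlier 8-week alternate-day study: "decreased weight (~8% of baseline body weight". Spread evenly, 8% / 4 = 2% per 2 weeks (compounded, 1 − 0.92^(1/4) = 2.06%).
- Section 4.a.1, rationale for the control condition: 6.5 kg lost over 8 weeks on 5-2 CR in a cited trial. Baseline weight is not given. Assuming 80-100 kg, this is 6.5/100 = 6.5% to 6.5/80 = 8.1%, or about 1.6-2.0% per 2 weeks.
- Section 4.a.2: "Weight loss for 5-2 CR is expected to be about 2% per week based on our previous work", which gives 2 × 2% = 4% per 2 weeks (compounded, 1 − 0.98² = 3.96%).

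The first two agree. The third implies 8 × 2% = 16% over 8 weeks, twice the 8% that the Introduction reports, although both statements cite the same earlier study (reference 39).

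No standard deviation is given. Assume a normal 2-week loss with a mean of 2% and an SD of 1.0 to 1.5 percentage points, and take the arm size from section 10.b ("There will be 20 participants in each group"):

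- SD 1.0: P(loss > 5%) = 1 − Φ((5 − 2)/1.0) = 1 − Φ(3.00) = 0.0013; × 20 = 0.03 participants.
- SD 1.5: 1 − Φ((5 − 2)/1.5) = 1 − Φ(2.00) = 0.023; × 20 = 0.46 participants.

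Both are below 1 of 20 per 2-week interval.

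**The case against.** The strongest reply is that the gap exists only if the trigger is read apart from its neighbour. The removal sentence speaks of loss in the range or above it continuing, which presupposes that such loss has already been noticed and followed. Together the two sentences read as one escalation rule with a floor near 4%, and staff would probably apply them that way. This stands, and it is why the point is a wording error and no more.

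A second reply is that a fast loser is not left unobserved. Section 8.a carries a general undertaking to watch weight loss, weight is taken every 2 weeks, symptoms are asked about at the remote contacts in between, and adverse events are sought at every contact. This also stands as a limit on the consequence. It does not close the literal gap, because none of these provisions requires an interim weighing.

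A reader might infer that the plan deliberately exempts larger losses, or that fast losers go without safety monitoring. The documents support neither. The removal sentence expressly reaches larger losses, and the contacts just listed continue for everyone.

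**Conclusion.** The point holds as a minor wording error in a safety threshold, at the lowest severity. As written, a first 2-week loss above 5% in the 5-2 CR arm starts no required weekly weighing, while a loss of 4.5% does. The intended meaning, 4% as a floor, is fairly clear from the next sentence.

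The consequence is at least one interim weighing, and at most those at weeks 3, 5 and 7. The removal rule can still act at the next 2-weekly visit.

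The number affected cannot be derived from the documents. Fewer than 1 of 20 per interval is the likely order at the pace of the cited 8-week results. It rests on an assumed SD of 1.0-1.5 points, normality, and loss spread evenly over the 8 weeks; faster early loss would raise it.

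A reader who starts from the 2% per week in section 4.a.2 might infer a larger problem. With a mean of 4%, the same assumptions give 1 − Φ(1.00) = 0.159 (3.2 of 20) to 1 − Φ(0.667) = 0.252 (5.0 of 20). Those figures should not be relied on. They need the same assumed SD, and a rate that conflicts with both 8-week results quoted elsewhere in the protocol. The textual defect does not depend on either estimate.

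**What to change.** In the trigger sentence of section 8.a, replace 4-5% with 4% or more and keep the rest of the sentence. Leave the removal sentence unchanged, since it already reaches larger losses.

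The cost is one wording change. Participants who lose 4-5% already get weekly visits, so any added weight checks fall only on those who lose more than 5% in 2 weeks. Under the assumptions above that is fewer than 1 participant per interval at the cited pace, and it can never exceed the 20 in the arm. Design, sample size and analysis are untouched.

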Rationale for control condition: We wish to implement a low intensity form of dietary intervention as an active placebo, by providing published material on “healthy living” diet to both groups. In general, counseling has very modest effects on body weight, if any. For example, Noda and colleagues⁹¹ examined weight loss over 8 weeks among participants who initially received 30-60 minutes of dietary counseling (n=44) vs. no counseling (n=47). Whereas the dietary counseling group showed modest weight loss (-0.6 kg) compared to baseline and weight in the no counseling group did not change (0 kg), there was no overall significant effect of Intervention Group. Six months of intensive dietary counseling, defined as weekly consultation for the first month and biweekly thereafter, led to modest weight loss (-2.5 kg)⁹² – in this study, we will implement a much less intensive form of dietary counseling. Therefore, dietary counseling alone is not an effective way for achieving weight loss. By contrast, Harvie et al.⁴⁰ found that 8 weeks of 5-2 CR led to a reduction of 6.5 kg. In addition to providing an active placebo, implementing the same dietary counseling to both groups, we intend to make the 5-2 CR group’s diet during non-CR days less variable and similar to that of the “Healthy living” group. Finally, by offering an intervention to control subjects, we intend to increase their motivation for completing the study. Counseling is routinely used as a control in studies implementing behavioral interventions, such as diet and exercise.⁹³

Although, we do not wish to implement detailed dietary counseling besides providing subjects with published material and reviewing it with them, the study Investigators have received advice by long-time collaborator at the US Department of Agriculture’s Beltsville Human Nutrition Research Center [name]. The Center is specialized in testing novel dietary interventions and implementing comprehensive behavioral interventions to ensure compliance. Study investigators and the Clinical Research Coordinator have become acquainted with their methods and will continue to consult with them throughout this study whenever applicable. The Clinical Research Coordinator or the PI will review the informational materials with participants and provide any necessary clarifications.

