	1 Day 3-hours	Day 1 7-9 hours	Day 2 optional	1 Day 1-hour	Day 1 7-9 hours	Day 2 optional
Procedures	Screening	Baseline		Compliance (Outpatient)	Outcome	
Informed Consent	X					
History and Physical (MMSE Visit 1 only)	X				X	
Review Inclusion/Exclusion Criteria	X	X				
Symptoms Review Questionnaire	X	X			X	
PANAS, RAND SF-36		X		X	X	
Cognitive Testing		X			X	
MRI		X			X	
Accelerometers	X				X	
Vital Signs	X	X		X	X	
Anthropometric measurements	X	X		X	X	
Urine Drug Screen	X					
Urine Pregnancy test	X	X			X	
Fasting Blood Draw	X	X		X	X	
Mixed Meal Tolerance Test		X			X	
Lumbar Puncture		X			X	
Dispense Diet Shakes (5-2 CR Group)		X		X		
Dietary Counseling-ALL Groups		X		X		
Meals / Snacks		X		X	X	
Follow-up Phone Call or Email				Weeks 1, 3, 5, 7	Follow-up	
Payment	\$50.00	\$350.00		\$150.00*	\$500.00	

Table 2: Laboratory

	Visit 1	Visit 2		Visit 3, 4, 5	Visit 6	
		Week 0		Weeks 2, 4, 6	Week 8	
	1 Day 3-hours	Day 1 7-9 hours	Day 2 optional	1 Day 1-hour	Day 1 7-9 hours	Day 2 optional
Laboratory	Screening	Baseline within 4 weeks of Screening Visit		Compliance (Outpatient)	Outcome	
Clinical Labs: CBC with differential, CMP, HbA1c, Phosphate, Magnesium, TSH, Liver Panel, Lipid Panel, Uric Acid, PT/INR, PTT, insulin, HIV, HBV, HCV	X					
Research Lab: Insulin	X					
Clinical Labs: CBC and PT/INR, PTT		X				
Research Labs: AD Biomarkers, Cytokines/Chemokines, Neurotrophic Factors, Exosomes, Oxidative Stress Biomarkers, gene expression and DNA methylation, WBC differential counts, β -hydroxybuterate		X				
CSF		X			X	
Research Labs: β -hydroxybuterate, gene expression and DNA methylation, WBC differential counts, plasma sample for AD Biomarkers, Cytokines/Chemokines, Neurotrophic Factors, Exosomes, Oxidative Stress Biomarkers				X		
Clinical Labs: CBC with differential, CMP, HbA1c, Phosphate, Magnesium, TSH, Liver Panel, Lipid Panel, Uric Acid, PT/INR, PTT, insulin					X	
Research Labs: AD Biomarkers, Cytokines/Chemokines, Neurotrophic Factors, Exosomes, Oxidative Stress Biomarkers, gene expression and DNA methylation, WBC differential counts, insulin, β -hydroxybuterate					X	

Amount of Blood	28 ml	168 ml	62 ml/visit	174 ml
-----------------	-------	--------	-------------	--------

4.d.2. Baseline visit

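### The expected 2% weekly weight loss in 4.a.2 is about twice what the protocol's own results support and would sit on the 8.a safety trigger; 8.a also leaves removed participants without an Outcome Visit

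*Combined protocol and SAP*

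**What the plan says.** Section 4.a.2 (Compliance) states: "Weight loss for 5-2 CR is expected to be about 2% per week based on our previous work". It then says that a progressive fall in weight "persisting in the 5-2 CR group over 8 weeks suggest compliance to 5-2 CR".

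The Introduction describes the study cited for that rate. After 8 weeks of alternate-day restriction it lists "decreased weight (~8% of baseline body weight". The rationale for the control condition in 4.a.1 adds a trial of the 5-2 regimen itself, in which "8 weeks of 5-2 CR led to a reduction of 6.5 kg".

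Section 8.a schedules weekly safety visits "If a participant on 5-2 CR loses 4-5% of their body weight within a 2-week period between visits". It continues: "If weight loss in that range or greater continues to occur, participants will be removed from the study".

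Sections 4.d.1 and 4.d.5 place the Outcome Visit only at the end of the 8 weeks. Neither 4.e nor 8.a describes an outcome assessment for someone taken off early. Section 10.b says: "Enrollment will continue and withdrawals will be replaced until we have acquired complete data from 40 participants". Section 3.a also replaces withdrawals; 4.a speaks only of voluntary dropouts, but its target of 40 with complete data leads to the same result.

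**The concern.** The protocol gives two rates for what it presents as the same prior work, and they differ by a factor of two. The higher one makes the same weight loss both a sign of compliance (4.a.2) and a reason for extra safety visits and then removal (8.a).

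The removal rule has two weaknesses of its own. First, visits become weekly after the trigger, but the text does not say whether 4-5% is then counted per week or per 2 weeks, so staff could apply it differently. Second, removal depends on a response after randomisation, is written for one arm only, and is followed by replacement. The completers in the 5-2 CR arm would then lack the participants who lost most weight, which is not a comparison of the groups as randomised.

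**Working it through.** **1. Does 2% per week reproduce from its source?** Input: about 8% in 8 weeks (Introduction).
- Linear: 8 / 8 = 1.0% per week.
- Compound: 1 − 0.92^(1/8) = 1.04% per week.
- In the other direction, 2% per week for 8 weeks is 2 × 8 = 16% linear, or 1 − 0.98^8 = 14.9% compound, against about 8% reported.

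It does not reproduce either way.

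**2. Does the 5-2 trial support it?** Input: 6.5 kg in 8 weeks (4.a.1). That section gives no baseline weight, so 70-120 kg is assumed.
- 70 kg: 6.5 / 70 = 9.3%; / 8 = 1.2% per week; / 4 = 2.3% per 2 weeks.
- 120 kg: 6.5 / 120 = 5.4%; / 8 = 0.7% per week; / 4 = 1.4% per 2 weeks.
- To reach 2% per week, baseline weight would have to be 6.5 / 0.16 = 41 kg (linear) or 6.5 / 0.149 = 44 kg (compound), which is implausible with BMI of at least 27.

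**3. Position against the trigger of 4-5% in 2 weeks.**
- At 2% per week: 4.0% linear, or 1 − 0.98² = 3.96% compound. This is the lower edge of the trigger.
- At 1% per week: 2.0%, half the lower edge.

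**4. How many would be removed at about 1% per week?** The documents give no spread. Assume 2-week losses are normal with mean 2.0 points and SD 1.0 or 1.5. Read removal as two consecutive 2-week losses of at least 4% by week 6. Let p = P(loss ≥ 4) in one interval.
- SD 1.0: p = P(Z ≥ 2.00) = 0.0228. SD 1.5: p = P(Z ≥ 1.33) = 0.0912.
- If a person's intervals are independent, removal = 2p² − p³ = 0.0010 (SD 1.0) or 0.016 (SD 1.5).
- If each person loses the same amount in every interval, removal = p = 0.023 or 0.091.
- Midway (half the variance between persons), simulation gives about 4% at SD 1.5.

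The range is 0.1-9% of the arm, or 0-1.8 of 20. At the 70 kg edge of step 2 (mean 2.3), the highest combination is P(Z ≥ 1.13) = 0.13, or 2.6 of 20. If 4% is instead counted in a single later week, simulated removal at 1% per week is 0-0.2%.

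**5. Effect on the retained group.** In the worst combination of step 4 (SD 1.5, identical intervals), the mean 2-week loss of those retained is 2 − 1.5 × 0.164 / 0.909 = 1.73, or 6.9% over 8 weeks against 8%. In the mildest it is 8.0%.

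**6. What this could mean for power.** The plan's calculation in 10.b has λ = f² × N × 2 / (1 − 0.4) = 0.09 × 40 × 2 / 0.6 = 12. On 38 df this gives 0.92 for the F test and 0.96 one-tailed, consistent with its claim of over 90%. If f were proportional to weight loss, which is an assumption, the worst combination gives f = 0.30 × 6.92 / 8 = 0.26, λ = 9.0 and one-tailed power 0.90.

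**The case against.** The strongest reply is that removal depends on the loss that occurs, not on the loss 4.a.2 expects. If 2% is a slip, nobody is removed because of it. That is right, and it limits the point. A reader might infer that the plan would remove a large share of the 5-2 CR arm and lose substantial power. The documents do not support this. It requires the 2% rate that the protocol's own results contradict, and it keeps f at 0.30 for a 16% loss, although the study behind the effect size saw BMI fall from 27.1 to 24.8, or about 8.5% (10.b).

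A reader might also infer that compliant participants would be judged non-compliant for missing 2%. That does not follow either. The weight criterion in 4.a.2 is a progressive decrease with no cut-off, β-hydroxybutyrate is the objective marker, and discontinuation for non-compliance in 8.a concerns keeping visits.

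Three further replies have force:
- The top of the range in step 4 needs both the larger SD and identical loss in every interval.
- Section 10.b reports body fat falling from 33.6 to 30.6 kg by 3 months in the 5-2 trial. This is fat rather than weight, but it hints at slower loss and puts the trigger further away.
- Missing follow-up applies equally to the other discontinuation reasons in 8.a, and the study calls itself an exploratory pilot.

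Plasma listed in Table 2 for weeks 2, 4 and 6 ("plasma sample for AD Biomarkers, Cytokines/Chemokines, Neurotrophic Factors, Exosomes") means on-diet samples would exist. They cannot show how much dilution occurs. They follow an 8-hour fast on the second restriction day. The Outcome sample follows a 12-hour fast and, by 4.d.5, falls on the first (4.d.1 says the second).

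None of this removes the contradiction in the rate, the undefined interval or the absent Outcome Visit.

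**Conclusion.** The concern holds in a limited form. That 2% per week conflicts with the protocol's own results is arithmetic and needs no assumption for the cited study. For the 5-2 trial it needs only a plausible baseline weight. The conflict with the 8.a trigger follows directly.

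The consequence for the estimate is small. At about 1% per week, roughly 0-2 of 20 in the 5-2 CR arm would be removed, given normal 2-week losses with SD 1.0-1.5 points. The bias is one-sided and probably dilutes the diet effect. That direction assumes that the primary ratio moves with weight loss; 10.b links fat mass to peripheral insulin sensitivity and carries the effect size over to the brain marker. The change is worth making because it is specific and cheap, and keeps the comparison as randomised.

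**What to change.** 1. In 4.a.2, change the expected loss to about 1% per week. Leave the 4-5% trigger and the weekly safety visits unchanged. Raising the trigger would loosen a safety limit, and the documents offer no evidence for that.
2. In 8.a, state that loss continues when there is a second 2-week loss of at least 4%.
3. In 8.a, replace removal from the study with stopping the 480 kcal days. Still invite the participant to the Week 8 Outcome Visit, at least for the fasting blood draw that gives the exosomal ratio, with lumbar puncture and MRI only where safe.
4. In 10.a, analyse these participants in their randomised arm and report the number of such stops. Align the replacement wording in 10.b with this.

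The cost is protocol wording and a visit already planned. By the payments in section 23, a full Week 8 visit is $500 and the itemised rate for a blood draw alone is $20, against $50 + $350 + 3 × $150 + $500 = $1,350 for a replacement who completes. These are participant payments only; staff time and procedures come on top.

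The downside is that a few 5-2 CR outcomes would be measured off diet. With a second qualifying interval ending at week 4 or 6, that is 4 or 2 weeks after stopping, which may itself dilute the effect a little.
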